Modulating Physiologic Effects Of Phospholipid Metabolism In Obesity And Diabetes

AIM 4: Composition and Function of Sarcoplasmic Reticulum in persons with the Metabolic Syndrome

**Comp-SR
Version 6
HRPO201311099
01/FEB/2021**

**Principal Investigator
[name]
Professor of Medicine**

**Sub-Investigators
[name]
Professor of Medicine**

**[name]
[name]
[name]
[name]**

**Administrative Coordinator
[name], BA, CCRP**

ROLE OF SARCOPLASMIC RETICULUM IN INSULIN SENSITIVITY AND THE METABOLIC SYNDROME

INTRODUCTION, BACKGROUND AND SIGNIFICANCE

Global death rates fell for most diseases over the last two decades. Diabetes is a glaring exception, with a 93% increase in the absolute number of deaths (second only to HIV/AIDS) and a 70% increase in global years of life lost between 1990 and 2010¹. With at least 1.5 billion overweight people in the world, a third of whom are obese², diabetes and premature death are certain to accelerate. While exercise has been shown to prevent diabetes and is a proven treatment for the metabolic derangements that occur in diabetes³, persons with the metabolic syndrome, pre-diabetes and diabetes often have poor exercise tolerance⁴. While overall lack of fitness is multi-factorial, reduced exercise performance may be related to fuel metabolism in skeletal muscle in susceptible individuals, including those with diabetes⁵⁻⁷. Exercise has been shown to improve metabolism of glucose and reduce insulin resistance in skeletal muscle, but the role of lipid metabolism to insulin sensitivity and exercise performance is not well understood. This study is a pilot that will explore the role of lipid metabolism in key metabolic pathways in skeletal muscle. The overall goal is to understand the abnormalities that occur in lipid metabolism in sedentary persons with the metabolic syndrome compared to controls without the metabolic syndrome who are normal weight and sedentary. This study will add to our understanding of how lipid metabolism contributes to insulin sensitivity and function in skeletal muscle.

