Study Design. We will perform a cross-sectional study of age-matched, sedentary lean controls and individuals with the metabolic syndrome, recruited in part from a large database of subjects screened for our recently completed clinical trial (manuscript in preparation) involving metabolic syndrome (NCT00455403).

Eligibility Criteria

Control subjects

Inclusion:

1. Sedentary: No routine exercise; walking <10,000 steps per day
2. Age >18 and <65
3. Body Mass Index (BMI) <32
4. Healthy by physical exam (patient is devoid of major acute or chronic illness)
5. No significant abnormality in screening labs

Exclusion:

1. Currently on any significant prescription medications other than oral contraceptives in women
2. Currently Pregnant
3. Current Tobacco use

Subjects with the Metabolic Syndrome**Inclusion**

1. Sedentary: No routine exercise; walking <10,000 steps per day
2. Age >18 and <65
3. Body Mass Index (BMI) >30
4. Meet at least three of the following ATP III criteria for the metabolic syndrome:
 - a. waist circumference > or = 40 inches in men, > or = 35 inches in women
 - b. blood triglycerides > or = 150 mg/dL
 - c. blood HDL cholesterol <40 mg/dL in men, <50 in women
 - d. blood pressure > or = 130 mmHg systolic, or > or = 85 mmHg diastolic
 - e. fasting blood sugar > or = 100 mg/dL

Exclusion

1. Diagnosed with Type 2 diabetes, coronary artery disease, cancer, liver, lung, or kidney disease or any other major illness
2. Currently on any significant prescription medications other than:
 - a. oral contraceptives in women
 - b. More than two standard medications for stage 1 hypertension in men or women (blood pressure 140-159/90-99)
3. Currently Pregnant
4. Current Tobacco use

Study Plan and Procedures

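### No control criterion explicitly excludes people who meet the ATP III definition; whether they are kept out depends on an undefined reading of a significant laboratory abnormality

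*Combined protocol and SAP*

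**What the plan says.** The Introduction sets the overall goal as a comparison with "controls without the metabolic syndrome who are normal weight and sedentary". The Study Design paragraph describes a "cross-sectional study of age-matched, sedentary lean controls and individuals with the metabolic syndrome". The Specific Aim and Anticipated Results sections say only that controls are lean; they do not mention syndrome status.

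Under Eligibility Criteria, the syndrome group needs a BMI above 30 and must "Meet at least three of the following ATP III criteria for the metabolic syndrome". Five items follow, each with a numeric cut-off: waist, triglycerides, HDL, blood pressure and fasting glucose.

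The control list has no counterpart. The criteria that could bear on syndrome status are:

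- inclusion 3: "Body Mass Index (BMI) <32"
- inclusion 4: "Healthy by physical exam (patient is devoid of major acute or chronic illness"
- inclusion 5: "No significant abnormality in screening labs"
- exclusion 1: "Currently on any significant prescription medications other than oral contraceptives in women"

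None gives a limit for waist, blood pressure, triglycerides, HDL or glucose.

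The Screening section and Schedule of Events show that every candidate, fasting, has waist and blood pressure measured and a lipid panel and CMP drawn.

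**The concern.** The study contrasts presence with absence of the metabolic syndrome, yet the written criteria test that status in one group only. In the other it rests on judgement about two undefined words. If people with mild syndrome enter as controls, the control mean probably moves towards the syndrome mean for SERCA activity and the PC/PE ratio, and a real difference becomes harder to detect. A report also could not rely on the eligibility criteria alone to say that controls were free of the syndrome.

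The risk is plausible. Recruitment draws partly on people screened for an earlier metabolic-syndrome trial, and the control BMI ceiling lies above the syndrome group's floor.

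**Working it through.** **1. Can inclusion 5 do the job?** Of the five ATP III items, three are laboratory values (triglycerides, HDL, glucose) and two are not (waist, blood pressure). The ways to meet at least three of five number 10 + 5 + 1 = 16. By laboratory items contained:

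| Laboratory items | Combinations |
|---|---|
| 0 | 0 |
| 1 | 3 |
| 2 | 9 |
| 3 | 4 |

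With only two non-laboratory items, no qualifying set can lack a laboratory one. If *significant* means past the ATP III cut-off, inclusion 5 excludes every ATP III case. If it means clinically marked, mild cases can pass. In the three one-laboratory combinations, control status can turn on a single marginal value.

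**2. A worked example.** Take a sedentary woman with BMI 28, waist 36 in, blood pressure 132/80 and HDL 48 mg/dL, untreated and otherwise unremarkable. She meets the waist (35 in or more), blood pressure (130 systolic or more) and HDL (below 50) items, so she has the syndrome by the protocol's definition. Her BMI bars her from the syndrome group. As a control she breaches no stated number; only the reading of *major* and *significant* could exclude her. At BMI 31 she qualifies for the syndrome group and might also pass as a control, and the eligibility lists do not say which applies.

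**3. The plan's sample size.** The inputs, from the Sample Size section, are a 25% lower SERCA activity, SD 0.445, 80% power, alpha 0.05 and 17 per group, with 25 enrolled. The control mean is not given in the text, so 17 can be neither confirmed nor refuted. Working backwards with a two-sided unpaired t-test, 17 per group at 80% power implies a standardised difference d = 0.991. That is a difference of 0.991 × 0.445 = 0.441 and a control mean of 0.441 / 0.25 = 1.76. If the control mean were 1.0, the normal approximation would give 2 × (1.960 + 0.842)² × 0.445² / 0.25² = 49.7, or 50 per group. The illustration below therefore takes d = 0.991 as the plan's implied value.

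**4. Illustrative dilution.** Let m be the share of controls with the syndrome and c the share of the full syndrome effect that they carry. With SD unchanged, the expected standardised difference is 0.991 × (1 − c·m). For example, at m = 20% and c = 1 it is 0.991 × 0.8 = 0.793. Power at 25 per group, two-sided t-test:

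| m (assumed) | Difference, c = 1 | Power, c = 1 | Difference, c = 0.5 | Power, c = 0.5 |
|---|---|---|---|---|
| 0 | 25% | 93% | 25% | 93% |
| 10% | 22.5% | 87% | 23.75% | 90% |
| 20% | 20% | 78% | 22.5% | 87% |
| 30% | 17.5% | 67% | 21.25% | 83% |

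At full effect, power stays at 80% or more until m is about 18%, or 0.18 × 25 = 4.5 controls. Both m and c are assumptions; the documents give neither.

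**The case against.** A reader might infer that nothing in the control list keeps people with the syndrome out. The documents do not support that. Inclusion 5 bears on every ATP III case, the fasting lipid panel and CMP are drawn to judge eligibility, and the only numeric laboratory limits in the protocol are the ATP III ones. Read at those limits, inclusion 5 excludes them all. Waist and blood pressure are also taken as part of the history and physical examination that inclusion 4 relies on. This stands, and it limits the point to a missing explicit rule. It does not close the gap: nothing links *significant* to those limits. If it were so linked, one HDL of 49 would exclude a woman with no other item, which is a different rule from absence of the syndrome.

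It can also be said that the Introduction already settles the example, because she is not without the syndrome, and that BMI 28 or 31 sits badly with normal weight or lean. That is fair as to intent, and the double eligibility at BMI 31 does come from the overlap between below 32 and above 30. But staff enrol from the eligibility list, and a lower BMI cap would still not test syndrome status.

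A reader might further infer that every contrast is biased towards no difference. For FAS that is not assured. The background reports higher FAS in obese healthy subjects and lower FAS in metabolically compromised obese subjects, so mild cases need not lie between the two group means.

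Finally, full dilution is close to an upper bound for a given m. Those most likely to slip through are borderline and often have a BMI of 30 or less, while the syndrome group needs a BMI above 30.

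**Conclusion.** The point holds as a gap between the stated control population and the criteria meant to deliver it. No control criterion explicitly excludes people who meet ATP III. Inclusion 5 may do so, wholly or in part, depending on how an undefined word is applied. A person with mild syndrome and a BMI of 30 or less who passes that judgement can enter only as a control.

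The likely effect is some dilution of the SERCA and PC/PE contrasts. Its size is unknown. The power losses shown rest on assumed shares, an unchanged SD and a standardised difference back-solved from the plan's own 17 per group.

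This should be fixed, but the documents do not support treating it as a bar to the study. It is an observational pilot, no misclassified control is shown, and the data needed to check are collected. Nor does it follow that a report could never describe the controls accurately, because syndrome status can be counted and reported for each of them.

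**What to change.** Add one control exclusion: *meets three or more of the ATP III criteria listed for the metabolic-syndrome group*. Apply it to the waist, blood pressure, triglycerides, HDL and fasting glucose already obtained at screening. In the same amendment, reconcile the control BMI limit with the descriptions of controls as lean and of normal weight.

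For controls already enrolled, count ATP III items from the screening data and report the counts. Leave those with three or more out of the control group in the primary comparison, under a rule fixed before outcome data are examined. Give the comparison of everyone enrolled as a sensitivity analysis.

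The cost is one eligibility line and a count from existing data, with no new measurements. The downside is a few more control screen failures, or a few controls lost from the primary comparison.

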But what does the sarcoplasmic reticulum have to do with blood sugar control? It turns out that insulin sensitivity is related to the activity of a protein that interacts with the sarcoplasmic reticulum, called sarco/endoplasmic reticulum ATPase (SERCA). The main function of SERCA is to store calcium in the sarcoplasmic reticulum in order to allow the muscle to relax. This resets the muscle to allow for repeated muscle contraction. However, SERCA is only functional when actively associated with the phospholipid layer of the SR. Calcium also seems to regulate insulin sensitivity in the muscle cell through the proteins CaMKK β , AMPK, and AS160 (Fig 4). When SERCA is not active and therefore calcium is not stored in the SR, muscle cells are more insulin sensitive. When SERCA is active and therefore calcium is stored away and not available in the cytosol of the cell, muscle cells are more insulin resistant.

[figure not shown]

Fig 1. FAS mRNA levels in human skeletal muscle. *P<0.05 vs. obese abnormal by Tukey's post hoc test. B. FAS mRNA in mice from Fig 1A of reference 4.

[figure not shown]

Fig 2. FAS and CEPT1 protein in skeletal muscle biopsies from 16 obese human subjects before and after 20% weight loss induced by gastric bypass.

How do these findings relate to the composition of the sarcoplasmic reticulum? Our studies have shown that SERCA has lower activity when the composition of the sarcoplasmic reticulum is comprised of more PC than PE. Mice that are artificially induced to have this altered SR composition through inactivation of FAS are found to have muscle weakness, but this is in exchange for improved blood sugar control. In normal mice with functioning FAS, the PE to PC ratio is preserved and muscle strength is normal, but at the cost of reduced insulin sensitivity. This suggests that insulin sensitivity may be determined by the ratio of PC to PE in muscle tissue, based upon the activity of SERCA. When there is more PC than PE, the activity of SERCA is lower and thus muscle function is compromised, but the cell's sensitivity to insulin is higher. Conversely, when there is more PE than PC, the activity of SERCA is higher and thus muscle function is preserved, but the cell's sensitivity to insulin is lower. Our conclusion from these observations is that the muscle cell sacrifices insulin sensitivity for muscle function when called upon to do so. The muscle cell's first priority is to contract, not to be sensitive to insulin.

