Muscle Biopsy. This procedure will be performed on the final visit. A member of the study team will obtain a sample of muscle tissue from the patient's thigh (vastus lateralis muscle). This involves numbing the skin with a local anesthetic (lidocaine), making a small (approximately the size of the dotted line ----- ; 1 cm) incision and removing a small (approximately 1/15th of an ounce) piece of muscle tissue. Each incision will be closed with a piece of sterile tape or a stitch, if necessary.

Sample Size Estimates and Statistical Analyses

There are no published data to guide estimates; to our knowledge, this type of study has never been done. If SERCA activity is 25% less in the metabolic syndrome, based on a standard deviation of 0.445 (Fig 14), 17 subjects per group are required (80% power, $\alpha=0.05$). We will enroll 25 for each group to account for assay problems and to increase power. For the mouse and cell culture studies, primary endpoints are clearly defined. Differences and variances from the first experiments will be used to estimate sample size (80% power, $\alpha=0.05$). All comparisons will use appropriate tests for parametric and nonparametric data. Suitable posttests will be used for multiple groups.

Anticipated Results, Alternative Approaches, Potential Problems and Benefits

Anticipated results of the study are lower SERCA activity and higher SR PC/PE ratio in people with metabolic syndrome compared to lean controls. We expect to find higher FAS and CEPT1 in metabolic syndrome skeletal muscle, reflecting activation of a phospholipid synthetic pathway attempting to replenish SR membrane composition disrupted by the obesity/high fat state.

Predicting relationships between insulin sensitivity and SERCA activity is difficult based on our mechanistic studies. The most insulin resistant could have the highest levels of FAS and CEPT1 despite lower SERCA activity in the setting of a higher PC/PE ratio. This would reflect the inability to synthesize key PE molecules due to the stress of lipid overload despite induction of the FAS-CEPT1 pathway.

An alternative approach could include euglycemic insulin clamps, but the Matsuda index is highly correlated with glucose disposal and much less invasive than a clamp.

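### The groups are age-matched by design, but neither the sample size nor the analysis text uses the matching; a linear model with group and age would recover the precision at almost no cost.

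*Combined protocol and SAP*

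**What the plan says.** The Study Design paragraph reads: "We will perform a cross-sectional study of age-matched, sedentary lean controls and individuals with the metabolic syndrome". It does not say whether matching is by pair or by frequency, and it gives no caliper or ratio. Under Eligibility Criteria both groups have the same limits, "Age >18 and <65", so age can vary widely within each group.

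The section Sample Size Estimates and Statistical Analyses supposes a difference, "If SERCA activity is 25% less in the metabolic syndrome", takes one standard deviation of 0.445, and concludes that "17 subjects per group are required" at 80% power and alpha 0.05. Enrolment is set at 25 per group. There is no within-pair correlation, no standard deviation of differences and no age term. The analysis text is "All comparisons will use appropriate tests for parametric and nonparametric data", followed by a remark on post-tests for multiple groups. The same paragraph also covers the mouse and cell culture studies.

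**The concern.** Matching on age balances age between the groups, so age contributes little to the error in the group difference. Age variation still sits inside the within-group standard deviation, and that is what an unpaired, unadjusted test divides by. If the outcome follows age in a similar way in both groups, the reported standard error is larger than the true one. Intervals are then too wide and p-values too large, and the effort spent on finding age-matched controls buys less than it should.

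The human outcomes affected are SERCA activity, the PC/PE ratio, FAS and CEPT1. Only SERCA activity is sized. The analysis text sorts tests by distribution and is silent on design, so a reader cannot tell whether the matching will be used.

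**Working it through.** **Inputs from the documents.** Standard deviation 0.445; 25% difference; 80% power; alpha 0.05 (sidedness not stated); 17 per group required; 25 per group enrolled; ages 19 to 64.

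**Assumed inputs.** The documents give no correlation r between age and any outcome, so r = 0, 0.3, 0.5 and 0.6 are used. Matching is taken as within 3 years, ages as uniform over 19 to 64, and the age slope as equal in the two groups unless stated.

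**The plan's own figure.** The 17 cannot be checked directly, because the control mean is not in the text and the cited figure is not available here. Working backwards with a two-sided two-sample formula:

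- Normal approximation: difference = 0.445 × (1.960 + 0.842) × √(2/17) = 0.428, so control mean = 0.428/0.25 = 1.71.
- t-test: difference = 0.441, so control mean = 0.441/0.25 = 1.76, and the standardised difference is 0.441/0.445 = 0.99 SD.

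So 17 fits an independent-sample calculation if the control mean is about 1.7 to 1.8. If 0.445 were instead a standard deviation of paired differences, 17 pairs would imply a control mean of about 1.29. The independent-sample reading is likely but not proven.

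**Standard error, exact matching.** Unadjusted: SD × √(2/n). True: SD × √(1 − r²) × √(2/n). The ratio is 1/√(1 − r²):

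- r = 0.3: 1/√0.91 = 1.048
- r = 0.5: 1/√0.75 = 1.155
- r = 0.6: 1/√0.64 = 1.250

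In the protocol's units at 25 per group, the unadjusted 95% half-width is 2.011 × 0.445 × √(2/25) = 0.253. With age in the model it is 0.242, 0.219 and 0.203 at these three values of r.

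**Simulation, 25 per group, matched within 3 years.**

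| r | SE too wide by | Type I error, unadjusted | Type I error, age in model |
|---|---|---|---|
| 0 | none | 5% | 5% |
| 0.3 | 4-5% | about 4% | about 5% |
| 0.5 | 15% | 2.5% | about 5% |
| 0.6 | 24% | 1.5% | about 5% |

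**Looser matching.** If only the group mean ages agree within 5 years, the excess is about 3% at r = 0.3 (type I error 4.4%) and 7% at r = 0.5 (3.2%).

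**Power at 25 per group, unadjusted against age in the model.**

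| True difference | r = 0.3 | r = 0.5 |
|---|---|---|
| 0.99 SD (implied by 17 per group) | 94% to 95% | 95% to 98% |
| 0.81 SD (gives 80% at r = 0) | 81% to 84% | 83% to 90% |

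The second row is an illustration of a smaller difference, not the plan's assumption.

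**Unequal age slopes.** With r = 0.5 in one group and 0 in the other, unadjusted type I error is about 5%, so nothing is too wide. With r = 0.5 and −0.5 it is about 8%. A model with one common age slope does not repair that (7.6%).

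**The case against.** A reader might infer that the plan specifies independent-sample tests. It does not. No test is named, and a paired t-test and a signed-rank test are also parametric and nonparametric tests. The sizing per group points towards independent samples but does not settle it. This objection stands: the point is that the matching is not carried into the sizing or analysis text, and the error follows only if unpaired, unadjusted tests are used.

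A reader might also infer that the standard error is too wide whenever an outcome varies with age. That is too strong. It needs a similar age trend in both groups; with opposite trends the unadjusted interval is too narrow.

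Third, it is tempting to say that the loss could decide the study's answer. For SERCA activity the documents do not support this: at the difference implied by 17 per group, unadjusted power at 25 per group is already about 93% or more. The form of matching and r are both assumptions, the study calls itself a pilot, and in the common-slope case the error is conservative.

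What remains is that the design fixes a factor which the analysis text leaves unused, although using it is nearly free.

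**Conclusion.** The point holds in a conditional form. The loss arises if unpaired, unadjusted tests are used and the age trend is similar in both groups. In that case precision is lost but false positives are not inflated. The loss runs from nothing at r = 0 to roughly a quarter of the standard error at r = 0.6, under matching within 3 years.

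For the sized endpoint the practical gain in power is small, if the 17 rests on a two-sided two-sample calculation. It would be larger if the true standardised difference is smaller than that calculation implies. The missing control mean leaves this open, and no separate sizing is given for PC/PE, FAS or CEPT1. This is a low-cost improvement to the analysis, not a flaw that threatens the study's validity.

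**What to change.** In Sample Size Estimates and Statistical Analyses, state that each human outcome is compared by a linear model with group and age (the matching factor), and that the group difference is reported with a two-sided 95% interval. In Study Design, state whether matching is by pair or by frequency, and how close.

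The model suits either form of matching. It also keeps subjects whose match is lost to an assay failure, which the protocol anticipates; a paired test would drop them. As an example, suppose 5 different subjects are lost in each group, leaving 15 intact pairs, with r = 0.5 and a difference of 0.81 SD. The age model then holds type I error at 5.0% and gives 82% power, against 72% unadjusted.

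The cost is wording, one degree of freedom and the assumption of a common age slope. Check that assumption with a group-by-age term. No new data are needed, since age is an eligibility criterion and date of birth is in the source documents. At r = 0 the model gives essentially the same power as the unadjusted test (about 80% for both at 0.81 SD).
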